3.3.2. ICH Listings

Number	Title	BMS Table number/File Name/BMS Template
8	Listing of Study Medication Exposure by Subject Listing Treated Subjects	Appendix 4.1.1A / rl-ex-lists1.lst / SS_EX_L_001
9	Listing of Adverse Event Treated Subjects	Appendix 6.5.1 / rl-ae-lists1.lst / GS_AEL_X_001
10	Listing of Adverse Event Unique Events Treated Subjects	Appendix 6.6.1 / rl-ae-uniques1.lst / GS_AE_L_U_002
11	Listing of Hematology - SI Units Treated Subjects	Appendix 7.1.1A / rl-lb-hems1.lst / SS_LB_L_001
12	Listing of Liver Function Tests - SI Units Treated Subjects	Appendix 7.1.1B / rl-lb-lfts1.lst / SS_LB_L_001
13	Listing of Enzymes - SI Units Treated Subjects	Appendix 7.1.1C / rl-lb-enzs1.lst / SS_LB_L_001
14	Listing of Renal Function Tests - SI Units Treated Subjects	Appendix 7.1.1D / rl-lb-rfts1.lst / SS_LB_L_001
15	Listing of Electrolytes - SI Units Treated Subjects	Appendix 7.1.1E / rl-lb-elcs1.lst / SS_LB_L_001

CONFIDENTIAL

AI468038/205891

Number	Title	BMS Table number/File Name/BMS Template
16	Listing of Fasting Lipids and Glucose – SI Units Treated Subjects	Appendix 7.1.1F / rl-lb-flgs1.lst / SS_LB_L_001
17	Listing of Hematology - US Unit Treated Subjects	Appendix 7.1.1G / rl-zl-hems1.lst / SS_LB_L_001
18	Listing of Liver Function Tests - US Unit Treated Subjects	Appendix 7.1.1H / rl-zl-lfts1.lst / SS_LB_L_001
19	Listing of Enzymes - US Unit Treated Subjects	Appendix 7.1.1I / rl-zl-enzs1.lst / SS_LB_L_001
20	Listing of Renal Function Tests - US Unit Treated Subjects	Appendix 7.1.1J / rl-zl-rfts1.lst / SS_LB_L_001
21	Listing of Electrolytes - US Unit Treated Subjects	Appendix 7.1.1K / rl-zl-elcs1.lst / SS_LB_L_001
22	Listing of Fasting Lipids and Glucose – US Unit Treated Subjects	Appendix 7.1.1L / rl-zl-flgs1.lst / SS_LB_L_001
23	Listing of Differences in Categorization of SI and US Laboratory Test Results Treated Subjects	Appendix 7.1.1M / rl-lb-diffunits1.lst / GS_LB_L_S_008
24	Listing of Pregnancy Test Treated Female Subjects	Appendix 7.1.1N / rl-lb-pregs1.lst / GS_LB_L_X_006
25	Listing of Electrocardiogram Treated Subjects	Appendix 7.3.1D / rl-eg-ecgs1.lst / GS_EG_L_X_001
26	Listing of Vital Signs Treated Subjects	Appendix 7.4.1B / rl-vs-lists1.lst / GS_VS_L_X_006

3.4. Virology

The Modified Treated Subjects population with available virology data will be used in the summaries and analyses. All treated subjects with available virology data will be used in the data listings.

3.4.1. Tables

Number	Title	BMS Table number/File Name/BMS Template
4.1	Baseline Genotypic Resistance Profile Modified Treated Subjects	Table S.3.9.1A / rt-gn-bases1.lst / SS_GN_T_001
4.2	Baseline Gag Polymorphisms at Selected Positions Modified Treated Subjects	Table S.3.9.1C / rt-gn-bslgags1.lst / SS_GN_T_002
4.3	Baseline Gag Polymorphisms at Selected Positions Modified Treated Subjects Identified as Protocol Defined Virologic Failures	Table S.3.9.1J / rt-gn-bslgagpdvfs1.lst / SS_GN_T_002
4.4	Newly Emergent Genotypic Resistance Profile Modified Treated Subjects with On-Treatment Genotypic Resistance Testing	Table S.5.10.1A / rt-gn-news1.lst / SS_GN_T_001
4.5	Newly Emergent Genotypic Resistance Profile Modified Treated Subjects Identified as Protocol Defined Virologic Failures	Table S.5.10.1B / rt-gn-newpdvfs1.lst / SS_GN_T_001
4.6	Emergent Gag Polymorphisms at Selected Positions Modified Treated Subjects with On-Treatment Gag Sequencing	Table S.5.10.1C / rt-gn-newgags1.lst / SS_GN_T_002
4.7	Emergent Gag Polymorphisms at Selected Positions Modified Treated Subjects Identified as Protocol Defined Virologic Failures	Table S.5.10.1D / rt-gn-newgagpdvfs1.lst / SS_GN_T_002

Number	Title	BMS Table number/File Name/BMS Template
4.8	Newly Emergent Phenotypic Resistance Profile Modified Treated Subjects with On-Treatment Phenotypic Resistance Profile	Table S.5.10.1G / rt-pn-news1.lst / SS_PN_T_001
4.9	Newly Emergent Phenotypic Resistance Profile Modified Treated Subjects Identified as Protocol Defined Virologic Failures	Table S.5.10.1H / rt-pn-newpdvfs1.lst / SS_PN_T_001

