7.3.2.4 Baseline Resistance

Phenotypic resistance to a drug is defined as a fold change (i.e., ratio of the 50% inhibitory concentration (IC₅₀) of the clinical isolate to the IC₅₀ of the reference strain) which is greater than the cut-off for reduced susceptibility.

The number of subjects with phenotypic resistance at baseline will be summarized for all treated subjects, for subjects who had on-study resistance testing done and for treated subjects that are identified as protocol defined virologic failures (see Protocol Section 5.4.1.3) using the following, mutually exclusive categories:

- No resistance to drugs in any class
- ≥ 1 NRTI
- ≥ 1 NNRTI
- ≥ 1 PI
- ≥ 1 INI
- ≥ 1 NRTI and ≥ 1 NNRTI
- ≥ 1 NRTI and ≥ 1 PI
- ≥ 1 NRTI and ≥ 1 INI
- ≥ 1 NNRTI and ≥ 1 PI
- ≥ 1 NNRTI and ≥ 1 INI
- ≥ 1 PI and ≥ 1 INI
- ≥ 1 NRTI and ≥ 1 NNRTI and ≥ 1 PI
- ≥ 1 NRTI and ≥ 1 NNRTI and ≥ 1 INI

- ≥ 1 NRTI and ≥ 1 PI and ≥ 1 INI
- ≥ 1 NNRTI and ≥ 1 PI and ≥ 1 INI
- ≥ 1 NRTI and ≥ 1 NNRTI and ≥ 1 PI and ≥ 1 INI

The number of subjects with phenotypic resistance will also be summarized by class and drug name.

The genotypic resistance profile at baseline will be summarized by treatment arm for all treated subjects, for subjects who had on-study resistance testing done and for treated subjects that are identified as protocol defined virologic failures. Tabulations will present genotypable isolates, those with PI substitutions from genotypable isolates, those with selected RT substitutions from genotypable isolates, and those with integrase substitutions from genotypable isolates using the most current version of the International AIDS Society-USA (IAS-USA) list (see [APPENDIX 2](#)). The genotypic resistance profile at baseline will also be summarized by baseline HIV subtype for all treated subjects.

In addition, baseline gag polymorphisms at positions 362, 364, 369 and 370 (relative to the wild type HxB2) will be summarized by treatment arm. This list of positions might be updated. The summary will report single mutations and combinations of mutations. The baseline gag polymorphisms at selected positions will also be summarized by baseline HIV subtype for all treated subjects.

Any deviation from the wild type virus (HxB2) in baseline gag sequencing will be summarized for treated subjects by treatment arm. This summary will also be provided by baseline HIV subtype.

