The maximum change from baseline in BMS-955176 IC₅₀ and the maximum BMS-955176 fold change IC₅₀ (FC-IC₅₀) through Week 96 will be summarized for all treated subjects with on-treatment phenotypic resistance profile. In addition, the proportion of subjects with a > 3 fold increase from baseline in BMS-955176 FC-IC₅₀ (i.e., BMS-955176 FC-IC₅₀ on-treatment divided by BMS-955176 FC-IC₅₀ at baseline > 3) will be summarized. The Gag polymorphisms will be summarized for subjects with a > 3 fold increase from baseline in BMS-955176 FC-IC₅₀. These summaries will use all of the data present in the database at the time of lock.

Newly emergent Gag polymorphisms at the selected positions will be summarized by treatment arm for treated subjects with on-treatment resistance testing done, overall and by baseline HIV subtype. In addition, any newly emergent Gag deviation will be summarized for treated subjects with on-treatment resistance testing done, overall and by baseline HIV subtype.

All summaries described in this section will also be provided for treated subjects that are identified as protocol defined virologic failures.

Protocol Defined Virologic Failure (PDVF) is defined by a subject meeting one of the following criteria (see Protocol, Section 5.4.1.2):

- Confirmed $> 1 \log_{10}$ c/mL increase in HIV-1 RNA at any time above nadir level where nadir is ≥ 40 c/mL
- Confirmed HIV-1 RNA ≥ 400 c/mL after Week 24
- Confirmed HIV-1 RNA ≥ 40 c/mL if prior suppression to < 40 c/mL
- Failure to have the last on-treatment HIV-1 RNA to < 400 c/mL within Week 24, 48, or 96 week snapshot window
- Failure to achieve $> 1 \log_{10}$ c/mL decrease in HIV-1 RNA by Week 8

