2. FINAL ANALYSIS

Per the company decision to end this study prior to all subjects reaching the primary endpoint, a simplified approach for the final report has been proposed by the project team. Hence the final analyses for AI468048 study as described in this appendix will be performed on subjects who were enrolled into this study, regardless of study stage, and will supersede what have been previously stated in the finalized BMS RAP Version 2.0. In addition, due to the GCP non-compliance of Site $\frac{PP}{D}$ ([name] in Chile) with ICH GCP E6 (R2) Guidelines, data obtained from this GCP non-compliant site will not be included in the final analyses (e.g., summary tables of selected efficacy and safety data); however, subject data listings will include all subjects enrolled in this study. Subject data listings for the GCP non-compliant Site $\frac{PP}{D}$ will also be provided.

The details of the final reporting and analysis plan are described as below:

1) Analysis Populations

Due to the GCP non-compliance of Site $\frac{PP}{D}$ data obtained from this GCP non-compliant site will be excluded in the final analyses.

Populations for Analyses for this synoptic report are defined as follows:

- Enrolled subjects are those who signed an informed consent form and were assigned a Patient Identification number (PID).
- Randomized subjects are enrolled subjects who received a treatment assignment from the IVRS and will be used in subject data listings as specified.
- Modified Randomized Subjects are enrolled subjects who received a treatment assignment from the IVRS, excluding subjects from Site $\frac{PP}{D}$. The modified randomized subjects will be used to assess subject disposition.
- Treated Subjects are randomized subjects who received at least 1 dose of study therapy and will be used in subject data listings as specified.
- Modified Treated Subjects are randomized subjects who received at least 1 dose of study therapy, exclude subjects from Site $\frac{PP}{D}$. Modified treated subjects will be used to assess demography and baseline characteristics,

protocol deviations, exposure, concomitant medication, efficacy, resistance and safety data.

- Pharmacokinetic (PK) population is defined as all treated subjects who have any available concentration-time data. The evaluable PK population is a sub-population including all treated subjects who have adequate PK profiles.

2) Demographic and baseline characteristic

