This report includes the analyses of demographics, baseline characteristics, and baseline resistance data based on Modified Treated Subjects population. Subject data listings will be based on Treated Subjects population.

The detailed outputs for demographic and baseline characteristic data are listed in the Section 3.1 of List of Displays for Study Population.

3) Simplified report on primary efficacy endpoint

Selected summaries and analyses on primary efficacy endpoint will be performed for this final analysis, based on Modified Treated Subjects population. Subject data listings will be based on Treated Subjects population.

The detailed outputs for primary efficacy endpoint data are listed in the Section 3.2 of List of Displays for Efficacy.

4) Secondary and Exploratory Efficacy Endpoints

Analyses for secondary and exploratory efficacy endpoints, including pharmacokinetic and quality of life endpoints, will not be performed except for HIV-1 RNA, CD4+ counts, and drug resistance endpoints (see additional details in Section 3.4, Virology) which are subject to availability of the data and will be analyzed based on Modified Treated Subjects population. There will be no subgroups and no multivariate analysis performed for secondary and exploratory efficacy endpoints for this final analysis. Subject data listings based on Treated Subjects population except PK data which will be based PK population.

The detailed outputs for primary secondary and exploratory efficacy endpoints are listed in the Section 3.2 of List of Displays for Efficacy.

5) Safety displays

Final safety analysis will be summarized based on Modified Treated Subjects population; however, subject data listings will be based on Treated Subjects population. Subject data listings will be based on Treated Subjects population.

The detailed outputs are listed in the Section 3.3 of List of Displays for Safety.

6) Virology

HIV drug resistance data will be summarized based on Modified Treated Subjects population. Subject data listings will be based on Treated Subjects population.

The detailed outputs for HIV drug resistance data are listed in the section of List of Display for Virology.

7) General

The display for TLFs will be based on BMS shells and will not utilize HARP for SAC.

The list of displays has been updated as shown below.

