271	Table S.5.10.3S	rt-gn-newgagpdvfbysubtypes12.lst	SS_GN_T_002	Emergent Gag Polymorphisms at Selected Positions By HIV Subtype Treated Subjects Identified as Protocol Defined Virologic Failures - Stage 1 and 2	WK96S2
272	Appendix 5.10.1B	rl-gn-gagontrts1.lst	SS_GN_L_002	Listing of Gag Polymorphisms at Selected Positions Treated Subjects with Baseline and On-Treatment Data - Stage 1	WK24S1, WK48S1 WK96S1, WK96S2
273	Appendix 5.10.2B	rl-gn-gagontrts2.lst	SS_GN_L_002	Listing of Gag Polymorphisms at Selected Positions Treated Subjects with Baseline and On-Treatment Data - Stage 2	WK24S2, WK48S2, WK96S2
274	Table S.5.10.1E	rt-gn-anygags1.lst	SS_GN_T_003	Newly Emergent Gag Deviations Treated Subjects with On-Treatment Gag Sequencing - Stage 1	WK24S1, WK48S1, WK96S1, WK96S2
275	Table S.5.10.2E	rt-gn-anygags2.lst	SS_GN_T_003	Newly Emergent Gag Deviations Treated Subjects with On-Treatment Gag Sequencing - Stage 2	WK24S2, WK48S2, WK96S2
276	Table S.5.10.3E	rt-gn-anygags12.lst	SS_GN_T_003	Newly Emergent Gag Deviations Treated Subjects with On-Treatment Gag Sequencing - Stage 1 and 2	WK96S2

No.	Table No.	Output File Name	Template ID	Title and Population	Purpose
277	Table S.5.10.1T	rt-gn-anygagbysubtypes 1.lst	SS_GN_T_003	Newly Emergent Gag Deviations By HIV Subtype Treated Subjects with On-Treatment Gag Sequencing - Stage 1	WK24S1, WK48S1, WK96S1, WK96S2
278	Table S.5.10.2T	rt-gn-anygagbysubtypes 2.lst	SS_GN_T_003	Newly Emergent Gag Deviations By HIV Subtype Treated Subjects with On-Treatment Gag Sequencing - Stage 2	WK24S2, WK48S2, WK96S2
279	Table S.5.10.3T	rt-gn-anygagbysubtypes 12.lst	SS_GN_T_003	Newly Emergent Gag Deviations By HIV Subtype Treated Subjects with On-Treatment Gag Sequencing - Stage 1 and 2	WK96S2
280	Table S.5.10.1F	rt-gn-anygagpdvfs1.lst	SS_GN_T_003	Newly Emergent Gag Deviations Treated Subjects Identified as Protocol Defined Virologic Failures - Stage 1	WK24S1, WK48S1, WK96S1, WK96S2
281	Table S.5.10.2F	rt-gn-anygagpdvfs2.lst	SS_GN_T_003	Newly Emergent Gag Deviations Treated Subjects Identified as Protocol Defined Virologic Failures - Stage 2	WK24S2, WK48S2, WK96S2
282	Table S.5.10.3F	rt-gn-anygagpdvfs12.lst	SS_GN_T_003	Newly Emergent Gag Deviations Treated Subjects Identified as Protocol Defined Virologic Failures - Stage 1 and 2	WK96S2

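### The final-analysis tables show emergent Gag changes only at the preselected positions and show no emergent phenotypic resistance to BMS-955176, although resistance endpoints are retained

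*SAP*

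**What the plan says.** SAP version 2.0, Section 7.3.2.4, defines the selected positions: "baseline gag polymorphisms at positions 362, 364, 369 and 370 (relative to the wild type HxB2) will be summarized by treatment arm". It adds: "This list of positions might be updated". No updated list appears in the document.

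Section 7.5.2.5 plans three kinds of on-treatment summary that bear on BMS-955176:
- emergent Gag polymorphisms at the selected positions;
- changes anywhere in Gag: "any newly emergent Gag deviation will be summarized for treated subjects with on-treatment resistance testing done, overall and by baseline HIV subtype";
- phenotypic resistance to BMS-955176: newly emergent resistance (fold change at most 3 at baseline and above 3 on treatment), the maximum IC50 change and maximum fold change, and a more than 3-fold increase from baseline.

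The same section repeats all of these for protocol-defined virologic failures. In the data presentation plan (Section 1.2), the any-position summary is Table S.5.10.1E, "Newly Emergent Gag Deviations Treated Subjects with On-Treatment Gag Sequencing - Stage 1", with S.5.10.1F for virologic failures. Newly emergent phenotypic resistance to BMS-955176 is S.5.10.1V, with S.5.10.1W for virologic failures.

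The final-analysis appendix, written after the decision to end the study early, states that its analyses "will supersede what have been previously stated in the finalized BMS RAP Version 2.0". Item 4 of its Section 2 drops secondary and exploratory efficacy analyses "except for HIV-1 RNA, CD4+ counts, and drug resistance endpoints", subject to availability of the data, and refers to Section 3.4 for detail. Section 3 numbers the virology tables 4.1 to 4.9, and Section 3.4.1 lists all nine. The emergent Gag tables among them are 4.6, "Emergent Gag Polymorphisms at Selected Positions Modified Treated Subjects with On-Treatment Gag Sequencing", and 4.7, which has the same content for virologic failures.

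**The concern.** BMS-955176 is described in SAP Section 1 as a novel maturation inhibitor, and the plan measures resistance to it with Gag sequencing and a Gag phenotypic assay. For such a drug, where in Gag resistance emerges is part of what the study can teach. A table confined to positions chosen in advance cannot show a new one. A virologic failure whose virus changed elsewhere in Gag would be counted as having no emergent polymorphism at the selected positions, which is correct but incomplete.

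SAP version 2.0 covered this in two ways: a table of any emergent Gag deviation, and phenotypic tables that would show lost susceptibility wherever the change lay. The appendix keeps resistance as an endpoint but removes both. What is lost is the comparison by arm, including against the TDF arms, for the study drug's own target.

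**Working it through.** The plan gives no figure to reproduce here and no arithmetic applies. The check is to match each of the nine virology tables in appendix Section 3.4.1, by source table number and template, to the shells in the data presentation plan, and ask two questions of each: (a) does it show emergent Gag changes outside the selected positions, and (b) does it show emergent phenotypic resistance to BMS-955176?

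| Final table | Source table, template | Content | (a) | (b) |
|---|---|---|---|---|
| 4.1 | S.3.9.1A, SS_GN_T_001 | Baseline PI, RT and integrase substitutions | No | No |
| 4.2 | S.3.9.1C, SS_GN_T_002 | Baseline Gag, selected positions | No | No |
| 4.3 | S.3.9.1J, SS_GN_T_002 | As 4.2, virologic failures | No | No |
| 4.4 | S.5.10.1A, SS_GN_T_001 | Emergent PI, RT and integrase substitutions | No | No |
| 4.5 | S.5.10.1B, SS_GN_T_001 | As 4.4, virologic failures | No | No |
| 4.6 | S.5.10.1C, SS_GN_T_002 | Emergent Gag, selected positions | No | No |
| 4.7 | S.5.10.1D, SS_GN_T_002 | As 4.6, virologic failures | No | No |
| 4.8 | S.5.10.1G, SS_PN_T_001 | Emergent phenotype by NRTI, NNRTI, PI and INI class | No | No |
| 4.9 | S.5.10.1H, SS_PN_T_001 | As 4.8, virologic failures | No | No |

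The result is 0 of 9 for each question. Four of the nine tables concern Gag, all at selected positions. Tables 4.8 and 4.9 do not fill the gap, because the shell has rows for four drug classes and none for a maturation inhibitor.

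On the Stage 1 numbering that the appendix uses, the outputs planned under Section 7.5.2.5 but not carried over are:
- any newly emergent Gag deviation: S.5.10.1E and 1F, and by subtype 1T and 1U;
- BMS-955176 phenotype: S.5.10.1K to 1P, 1V and 1W;
- emergent Gag polymorphisms in subjects with a more than 3-fold increase in fold change: S.5.10.1Q.

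The remaining final tables (1.1 to 1.5, 2.1 to 2.4 and the safety series) do not help. The shell for Table 1.4 carries BMS-955176 IC50 and fold change, but only at baseline.

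One further comparison is relevant. SAP Section 7.8 names a shorter set of integrated summaries for the final analysis. That set includes both any emergent Gag deviation and newly emergent phenotypic resistance to BMS-955176, so version 2.0 still kept both when it selected the outputs to integrate across stages.

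**The case against.** The strongest reply is that this was a deliberate and disclosed reduction. The study stopped early, the appendix announces a simplified report, and which secondary virology displays survive is partly a reporting choice. SAP Section 4.2 also defines the secondary resistance endpoint by the IAS-USA mutation list, which Tables 4.4 and 4.5 still serve. Any-position Gag change is a planned display in Section 7.5.2.5, not a listed endpoint. This stands as a reason to keep the point modest. It does not explain why the Gag tables that were kept are the ones least able to show something new, and the appendix gives no reason specific to Gag.

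A second reply is that the data may still be reported by subject. Other Listings are numbered 27 to 44 and only 27 to 36 are visible. Appendix Section 3.4 says that treated subjects with virology data will be used in listings, and the data presentation plan holds a ready listing of emergent Gag deviations. A reader might infer that the information is reported nowhere, but the documents do not support that.

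A third reply is that a table of sequence deviations does not by itself show resistance. That is right, and it is why the phenotypic tables belong in the remedy.

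Three other stronger readings should be avoided:
- The gap cannot be expressed as a share of Gag codons, because the length of Gag sequenced is not stated and 370 is a reference coordinate, not a codon count.
- The documents do not say that the any-position summary was planned because the position list was provisional. Section 7.5.2.5 gives no reason for it.
- Tables 4.6 and 4.7 would not report a subject with a change elsewhere as having no emergent Gag change. Their titles limit them to the selected positions.

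**Conclusion.** The point holds for the summary tables. The appendix retains drug resistance endpoints, yet no final table shows by arm an emergent Gag change outside positions 362, 364, 369 and 370, or emergent phenotypic resistance to BMS-955176. Both summaries were pre-specified in version 2.0.

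The size is 0 of 9 virology tables on each count. How many subjects this would affect cannot be judged from the document. It bears on the completeness of a retained secondary endpoint and leaves the primary result untouched, so it should be corrected but is not critical.

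The conclusion rests on three assumptions: that the numbering 4.1 to 4.9 is the full set of virology tables, as appendix Section 3 states; that the position list has not been extended outside this document; and that the final tables follow the cited shells. Listings 37 to 44 could soften the practical effect but would not supply a comparison by arm.

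**What to change.** Add S.5.10.1E (Modified Treated Subjects with on-treatment Gag sequencing) and S.5.10.1F (Modified Treated Subjects identified as protocol-defined virologic failures) to appendix Section 3.4.1, by treatment arm, beside Tables 4.6 and 4.7. Both use shell SS_GN_T_003. Preferably also add S.5.10.1V and S.5.10.1W (shell SS_PN_T_004), so that emergent phenotypic resistance to BMS-955176 is tabulated and any-position sequence changes can be read alongside it.

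State in the appendix which Gag positions count as selected at final analysis. If the omission is intended, say so, give the reason, and name the listings that hold the subject-level Gag and BMS-955176 phenotype data.

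The cost is two to four extra tables in a simplified report, taking the virology series from 9 to 11 or 13. The shells exist, and the any-position tables draw on the same Gag sequencing as Tables 4.6 and 4.7. The phenotypic pair depends on the Gag phenotype results being available, the condition the appendix already sets for resistance data.

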3.2 Secondary

- To assess the antiviral efficacy of BMS-955176 Arms, and TDF-containing regimens (TDF + ATV/r + DTG), by determining the proportion of treatment-experienced subjects with plasma HIV-1 RNA < 40c/mL at Weeks 48 and 96
- To assess the antiviral efficacy of BMS-955176 Arms, and TDF-containing regimens, by determining the proportion of treatment-experienced subjects with plasma HIV-1 RNA < 200c/mL at Weeks 24, 48, 96
- To assess the emergence of HIV drug resistance in samples selected for drug resistance testing
- To assess efficacy of BMS-955176 Arms, and TDF-containing regimens, by using the mean changes from baseline in log₁₀ HIV-1 RNA, CD4+ T-cell counts, and percentage of CD4+ T-cells
- To assess the safety and tolerability of BMS-955176 in treatment-experienced subjects by measuring frequency of SAEs and AEs leading to discontinuation
- To assess disease progression as measured by the occurrence of new AIDS defining events (CDC Class C events)
- To characterize the pharmacokinetics of BMS-955176 when co-administered with ATV (with or without ritonavir) and DTG in treatment-experienced HIV-1 infected subjects.

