7.5.2.4 Changes from Baseline in CD4+ and CD8+ T-cell Count over Time

CD4+ and CD8+ T-cell counts and changes from baseline will be summarized at each scheduled visit through Week 96 by treatment arm using observed values. The mean changes from baseline will be plotted at each scheduled visit through Week 96 by treatment arm, with error bars representing 1 standard error. The change from baseline in CD4+ and CD8/ T-cell counts at Week 24, 48 and 96 will be presented graphically using box plots. Also the percentage of CD4+ T-cells and changes from baseline will be summarized at each scheduled visit through Week 96. The change from baseline will also be provided for the subgroups identified for the primary analysis.

7.5.2.5 Newly-emergent Genotypic Substitutions, IC₅₀ Fold Changes from Baseline and Newly-emergent Gag Polymorphisms

Viral resistance is measured using the “PhenoSense GT plus Integrase” assay from Monogram (LabCorp). The PhenoSense GT plus Integrase is used to determine both genotypic and phenotypic resistance to Nucleoside Reverse Transcriptase Inhibitors (NRTIs), Non-Nucleoside Reverse Transcriptase Inhibitors (NNRTIs), Integrase Inhibitors (INIs), and Protease Inhibitors (PIs). The “PhenoSense Gag” assay is used for determining phenotypic susceptibility to BMS-955176. HIV-1 Gag sequencing data will be obtained from the NGS-Gag Quantitative Sequencing (QS) assay.

Genotypic substitutions and phenotypic resistance profiles focus on subjects with on-treatment isolates.

Newly emergent phenotypic resistance to a drug is defined as a baseline fold change \leq the cut-off for reduced susceptibility and an on-treatment fold change $>$ the cut-off for reduced susceptibility. The newly emergent phenotypic resistance profile (using all on-treatment isolates) will be tabulated by treatment arm for treated subjects with on-treatment resistance testing done.

Newly emergent phenotypic resistance to BMS-955176 is defined as a baseline fold change IC₅₀ ≤ 3 and an on-treatment fold change IC₅₀ > 3 . The newly emergent phenotypic resistance to BMS-955176 (using all on-treatment isolates) will be tabulated by treatment arm for treated subjects with on-treatment resistance testing done.

Newly emergent genotypic substitutions (using all on-treatment isolates) are tabulated by treatment arm for treated subjects with on-treatment resistance testing done. The presentation will be similar to the one for baseline genotypic substitutions.

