Table No.	Appendix 3.9.1D
Title 1	Listing of Baseline Gag Deviations from Wild Type Virus
Title 2	Treated Subjects - Stage 1
Programming notes	Please include only the pre-treatment assessments.

Parameter	Values
Template ID	SS_GN_L_003
Output File Name	rl-gn-gagbslanys2.lst
Purpose	WK24S2, WK48S2, WK96S2
Table No.	Appendix 3.9.2D
Title 1	Listing of Baseline Gag Deviations from Wild Type Virus
Title 2	Treated Subjects - Stage 2
Programming notes	Please include only the pre-treatment assessments.

Template SS_PN_T_001: Baseline Phenotypic Resistance Categories

	Group A N = XX	Group B N = XX	Group C N = XX	Group D N=XX
PHENOTYPIC TESTING AT BASELINE	XX/XX (XX.X)	XX/XX (XX.X)	XX/XX (XX.X)	XX/XX (XX.X)
PHENOTYPABLE	XX/XX (XX.X)	XX/XX (XX.X)	XX/XX (XX.X)	XX/XX (XX.X)
RESISTANCE CATEGORY				
NO RESISTANCE TO DRUGS IN ANY CLASS	XX/XX (XX.X)	XX/XX (XX.X)	XX/XX (XX.X)	XX/XX (XX.X)
≥1 NRTI	XX/XX (XX.X)	XX/XX (XX.X)	XX/XX (XX.X)	XX/XX (XX.X)
≥1 nNRTI	XX/XX (XX.X)	XX/XX (XX.X)	XX/XX (XX.X)	XX/XX (XX.X)
≥1 PI	XX/XX (XX.X)	XX/XX (XX.X)	XX/XX (XX.X)	XX/XX (XX.X)
≥1 INI	XX/XX (XX.X)	XX/XX (XX.X)	XX/XX (XX.X)	XX/XX (XX.X)
(≥1 NRTI) AND (≥1 nNRTI)	XX/XX (XX.X)	XX/XX (XX.X)	XX/XX (XX.X)	XX/XX (XX.X)
(≥1 NRTI) AND (≥1 PI)	XX/XX (XX.X)	XX/XX (XX.X)	XX/XX (XX.X)	XX/XX (XX.X)
(≥1 NRTI) AND (≥1 INI)	XX/XX (XX.X)	XX/XX (XX.X)	XX/XX (XX.X)	XX/XX (XX.X)
(≥1 nNRTI) AND (≥1 PI)	XX/XX (XX.X)	XX/XX (XX.X)	XX/XX (XX.X)	XX/XX (XX.X)
(≥1 nNRTI) AND (≥1 INI)	XX/XX (XX.X)	XX/XX (XX.X)	XX/XX (XX.X)	XX/XX (XX.X)
(≥1 PI) AND (≥1 INI)	XX/XX (XX.X)	XX/XX (XX.X)	XX/XX (XX.X)	XX/XX (XX.X)
(≥1 NRTI) AND (≥1 nNRTI) AND (≥1 PI)	XX/XX (XX.X)	XX/XX (XX.X)	XX/XX (XX.X)	XX/XX (XX.X)
(≥1 NRTI) AND (≥1 nNRTI) AND (≥1 INI)	XX/XX (XX.X)	XX/XX (XX.X)	XX/XX (XX.X)	XX/XX (XX.X)
(≥1 NRTI) AND (≥1 PI) AND (≥1 INI)	XX/XX (XX.X)	XX/XX (XX.X)	XX/XX (XX.X)	XX/XX (XX.X)
(≥1 nNRTI) AND (≥1 PI) AND (≥1 INI)	XX/XX (XX.X)	XX/XX (XX.X)	XX/XX (XX.X)	XX/XX (XX.X)
(≥1 NRTI) AND (≥1 nNRTI) AND (≥1 PI) AND (≥1 INI)	XX/XX (XX.X)	XX/XX (XX.X)	XX/XX (XX.X)	XX/XX (XX.X)

Parameter	Values
Template ID	SS_PN_T_001
Output File Name	rt-pn-bsls1.lst
Purpose	WK24S1, WK48S1, WK96S1, WK96S2
Table No.	Table S.3.9.1F
Title 1	Baseline Phenotypic Resistance Categories
Title 2	Treated Subjects - Stage 1

Parameter	Values
-----------	--------

Template ID	SS_PN_T_001
Output File Name	rt-pn-bsls2.lst
Purpose	WK24S2, WK48S2, WK96S2
Table No.	Table S.3.9.2F
Title 1	Baseline Phenotypic Resistance Categories
Title 2	Treated Subjects - Stage 2

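### The final analysis has no on-treatment summary table of phenotypic susceptibility to BMS-955176, and Tables 4.8 and 4.9 would count resistance to that drug alone as no resistance

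*SAP*

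**What the plan says.** The final-analysis appendix states that it "will supersede what have been previously stated in the finalized BMS RAP Version 2.0" (Section 2). Item 4 of that section says that secondary and exploratory analyses "will not be performed except for HIV-1 RNA, CD4+ counts, and drug resistance endpoints", subject to data availability. Item 6 adds: "HIV drug resistance data will be summarized based on Modified Treated Subjects population".

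Section 3 of the appendix numbers the virology tables 4.1 to 4.9, and Section 3.4.1 lists all nine. Phenotype appears in two of them. Table 4.8 is "Newly Emergent Phenotypic Resistance Profile Modified Treated Subjects with On-Treatment Phenotypic Resistance Profile", sourced from "Table S.5.10.1G / rt-pn-news1.lst / SS_PN_T_001". Table 4.9 is the same display in protocol-defined virologic failures.

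SAP version 2.0 planned more. Section 3.2 sets a secondary objective: "To assess the emergence of HIV drug resistance in samples selected for drug resistance testing". Section 7.5.2.5 gives BMS-955176 its own definition of emergent phenotypic resistance (baseline fold change at most 3, on-treatment fold change above 3) and commits to it: "The newly emergent phenotypic resistance to BMS-955176 (using all on-treatment isolates) will be tabulated by treatment arm". The same section adds the maximum change in IC50, the maximum fold change, and the proportion with a more than 3-fold increase.

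**The concern.** BMS-955176 is the novel agent in the trial. A reader of the final report will want to know how many subjects lost susceptibility to it, and the appendix expressly keeps resistance among the few endpoints still analysed. The phenotypic tables that remain describe the comparator and background classes only. Their first row, "NO RESISTANCE TO DRUGS IN ANY CLASS", reads as covering every drug, although the study drug is not among the drugs assessed. A subject whose virus became resistant only to BMS-955176 would sit in that row. Because that can happen only to a subject who received BMS-955176, any misreading favours the investigational arms.

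**Working it through.** No error rate or sample size is involved, so this is a cross-check of tables and shells.

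**1. Is the table list closed?** Section 3 of the appendix gives virology tables 4.1 to 4.9, which is nine. Section 3.4.1 lists nine: baseline genotype (4.1), baseline Gag (4.2, 4.3), emergent genotype (4.4, 4.5), emergent Gag (4.6, 4.7) and emergent phenotype (4.8, 4.9). The count agrees, so the pages not shown cannot hold a tenth virology table.

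**2. What can 4.8 and 4.9 show?** Both use shell SS_PN_T_001, set out in Section 4.3.2 of the data presentation plan. Apart from the testing counts, its rows are "NO RESISTANCE TO DRUGS IN ANY CLASS" and the combinations of NRTI, NNRTI, PI and INI. Four classes, each present or absent, give 2^4 = 16 outcomes: 1 (none) + 4 (one class) + 6 (two) + 4 (three) + 1 (all four) = 16. These are the 16 rows of the shell, and SAP Section 7.3.2.4 calls the categories mutually exclusive.

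BMS-955176 is absent from the cut-offs in SAP Table 9-3, and SAP Appendix 2 says that the supplied resistance status is for antiretrovirals other than BMS-955176. The specifications of S.5.10.1G and S.5.10.1H carry definition footnotes but no layout note that adds the study drug or alters the first row.

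**3. Where do subjects fall?**

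- Emergent resistance to BMS-955176 only: none of the four classes, hence the row "NO RESISTANCE TO DRUGS IN ANY CLASS".
- Emergent resistance to BMS-955176 and a PI: the PI-only row.

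In neither case does resistance to the study drug appear.

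**4. What was dropped?** The Stage 1 tables of on-treatment BMS-955176 phenotype in the data presentation plan, against the appendix:

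| Tables | Content | In appendix |
|---|---|---|
| S.5.10.1K, L | Maximum change in IC50 | No |
| S.5.10.1M, N | Maximum fold change | No |
| S.5.10.1O, P | More than 3-fold increase | No |
| S.5.10.1V, W | Baseline fold change ≤ 3 and on-treatment > 3 | No |

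Eight were planned and none is kept. The second table of each pair is restricted to protocol-defined virologic failures. S.5.10.1Q, the Gag table for subjects with a more than 3-fold increase, is also gone.

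**5. What remains on the study drug?** Table 1.4 keeps BMS-955176 IC50 and fold change at baseline only. Its fold-change row from 1 to below 5 also straddles the cut-off of 3 used in Section 7.5.2.5. Tables 4.6 and 4.7 give emergent Gag sequence at selected positions, which does not measure fold change.

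**The case against.** The strongest reply is that the reduction was declared. The company ended the study early, the appendix announces a simplified report that replaces version 2.0, and choosing which tables to carry forward is a judgement of scope. That stands to this extent: omitting version 2.0 tables is not in itself a contradiction. It does not answer the row label, nor why an appendix that retains resistance summarises on-treatment phenotype for every class except that of the study drug. SAP Section 7.8 had listed the phenotypic profile and phenotypic resistance to BMS-955176 as separate final outputs, so the profile table was not designed to cover both. The document history shows that the BMS-955176 summary was added in version 2.0.

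A second reply is that the row is correct in context. Section 7.5.2.5 assigns the four classes to the PhenoSense GT plus Integrase assay and BMS-955176 to the separate PhenoSense Gag assay, so any class means the four listed beneath. The counts are indeed right for what the table measures. The fault is a label that claims more, with no companion table to correct it.

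Several stronger readings are tempting, but the documents do not support them:

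- A reader might infer that all phenotypic information on BMS-955176 is lost. Baseline values remain in Table 1.4.
- A reader might infer that the secondary endpoint is not delivered. SAP Section 4.2 defines that endpoint by the IAS-USA mutation list, which Tables 4.4 and 4.5 address. The BMS-955176 phenotype was a further analysis under Section 7.5.2.5.
- A reader might infer that the report will contain no on-treatment BMS-955176 phenotype at all. Other listings run from 27 to 44 and only 27 to 36 are visible, so eight (37 to 44) are unseen and may hold subject-level results. They would not supply counts by arm.
- A reader might infer that resistance is understated in Arms 1, 3 and 4. The virology tables cite Stage 1 shells, and nothing in the documents shows that data exist for Arms 3 and 4.

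**Conclusion.** The point holds in this form. The final analysis keeps drug resistance but has no on-treatment or emergent summary table of phenotypic susceptibility to BMS-955176. Tables 4.8 and 4.9 would place a subject resistant to BMS-955176 alone among those with no resistance. The omission covers all eight planned Stage 1 tables. The number of subjects misread cannot be derived, because the documents give no fold-change results, but the direction is fixed: only arms given BMS-955176 can be understated. The misplacement follows from the shell's rows and is not stated in the plan. The conclusion assumes that 4.8 and 4.9 are produced from SS_PN_T_001 as specified.

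**What to change.** In appendix Section 3.4.1, restore S.5.10.1V and S.5.10.1W (newly emergent phenotypic resistance to BMS-955176, overall and in protocol-defined virologic failures) and S.5.10.1O (more than 3-fold increase). Run them on Modified Treated Subjects with available baseline and on-treatment BMS-955176 phenotype.

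In Tables 4.8 and 4.9, rename the first row *No resistance to NRTI, NNRTI, PI or INI*. If a BMS-955176 row is added there, place it outside the 16 mutually exclusive categories and use the Section 7.5.2.5 definition (baseline fold change at most 3, on-treatment above 3). Inside the 16 it would break their exclusivity.

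The cost is three short tables from shells already specified and one changed label. It depends on on-treatment PhenoSense Gag results being available, which the documents do not confirm.
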